### 851 **Other Assessments**

852 We will assess patient satisfaction by using the DTSQs at baseline and the DTSQc at the end-  
853 of-study, as recommended by Health Psychology Research.

854 For treatment satisfaction, subjects' responses to questions 1, 7 and 8 of the DTSQc will be  
855 used. A comparison of the score on the DTSQs from week 0 to week 24, as well as using the  
856 score on the other questions of the DTSQc, which would overcome the ceiling limitation of using  
857 the DTSQs by itself. The Diabetes Treatment Satisfaction Questionnaire Status (DTSQs) form  
858 will be administered at weeks 0, 12 and the DTSQc will be administered at week 26. The  
859 amplitude of the score on the DTSQc gives the degree of change in satisfaction, while the  
860 direction (positive or negative) will provide guidance on the preference of one treatment regimen  
861 over the other one.

862 For quality of life, we will use the "Treatment-related impact measures for diabetes" (TRIM-D)"  
863 in order to determine the impact of the type of therapy on this outcome. Subjects will be given  
864 the questionnaire at baseline, and weeks 12 and 26 to assess their quality of life and any  
865 potential impact of the treatment regimen .

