92 ***glycemic control, as measured by change in HbA1c (non-inferiority limit of 0.4%),***  
93 ***compared to treatment with basal-bolus insulin regimen in patients with poorly***  
94 ***controlled T2D (HbA1c  $\geq$ 9-15%).***

- 95 - Primary outcome: change in HbA1c from baseline after 26 weeks of treatment with  
96 IDegLira vs basal-bolus insulin (with metformin, unless contraindicated).
- 97 - **Hypothesis:** After 26 weeks of treatment, IDegLira will result in similar improvement in  
98 glycemic control compared to basal-bolus insulin therapy.

99 **Specific Aim 2:**

100 ***2. To determine whether treatment with IDegLira will result in lower rate of***  
101 ***hypoglycemic events and less glycemic variability (superiority), as measured by***  
102 ***continuous glucose monitoring (CGM), compared to basal-bolus insulin in patients***  
103 ***with T2D and HbA1c  $\geq$ 9-15%.***

- 104 - Patients with poorly controlled T2D randomized to IDegLira or basal-bolus (with  
105 metformin, unless contraindicated) will have a one-week blinded CGM study performed  
106 during follow-up visits at 1, 12, and 26 weeks as well as 8-point self-monitored blood  
107 glucose (SMBG). CGM will allow better detection of hypoglycemic events, particularly  
108 asymptomatic and nocturnal hypoglycemia. It will also provide critical information on  
109 time in glycemic range and glycemic variability.
- 110 - **Hypothesis:** IDegLira will result in less hypoglycemia and glycemic variability  
111 compared to basal-bolus insulin regimen.

112 **Specific Aim 3:**

113 ***3. To determine whether treatment with IDegLira will result in improved patient***  
114 ***satisfaction compared to treatment with basal-bolus in patients with T2D and high***  
115 ***HbA1c ( $\geq$ 9-15%).***

- 116 - Patients with poorly controlled T2D randomized to IDegLira or Basal-Bolus will  
117 complete the Diabetes Treatment Satisfaction Questionnaire (DTSQ) and Treatment-  
118 related impact measures for diabetes (TRIM-D) survey during follow-up visits.
- 119 - **Hypothesis:** Use of IDegLira is associated with higher patient satisfaction and  
120 adherence compared to a multiple-daily injection regimen with basal-bolus insulin.

122 **CURRENT STATUS OF WORK IN THE FIELD**

123 **Epidemiology and treatment of patients with poorly controlled T2D and HbA1c >9%**

124

125

126       Based on NHANES data from 2007-2010, up to   135   with Diabetes: US and Emory Data

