## 300 **STUDY DESIGN AND METHODS:**

301 The study is a 26-week, open-label, treat-to-target, two-arm parallel, randomized, controlled trial  
302 investigating the efficacy and safety of IDegLira versus basal-bolus insulin in patients with T2D.  
303 Patients with HbA1c  $\geq$  9% treated with oral antidiabetic agents and/or basal insulin therapy  
304 (TDD  $\leq$  50 units) will be randomized in a 1:1 manner to receive IDegLira or basal-bolus insulin  
305 regimen (plus metformin unless contraindicated), as shown in Fig 2. Subjects will have contact  
306 with the study team via clinic visits or phone contacts for a total of 29-weeks, as shown in the  
307 figure below (Fig 2 and Table 1).

308  
309 Figure 2. Study design

311 Legend: OAD: Oral anti-diabetic agents, EOT: End-of-treatment, FUP: Follow-up safety visit

312  
313 Visits will be distributed as follows: initial screening visit/CGM insertion (visit 1), 2 weeks of  
314 screening/run-in period, randomization visit (visit 2), 26-week treatment period (visits 4-18), and  
315 a follow-up safety visit after the end the 26-weeks treatment period (visit 19). Subjects will have  
316 contact with the study team via clinic visits or phone contacts for a total of 9 clinic visits and 9  
317 telephone contacts. This study will include patients with a known history of T2D, age 18-80,  
318 treated with oral antidiabetic agents including metformin, sulfonylurea, repaglinide/nateglinide,  
319 pioglitazone, DPP4 inhibitors, SGLT2 inhibitors, (monotherapy + basal insulin) or in combination  
320 therapy (2-3 agents), and/or on basal insulin at a total daily dose (TDD) of  $\leq 50$  units.

321 Participants previously using basal insulin [neutral protamine hagedorn (NPH), mixed insulin,  
322 detemir or glargine insulin], will be switched to study-provided Degludec or IDegLira and/or  
323 Aspart pens. Metformin will be continued at same dose during the study, unless contraindicated.  
324 Patients previously treated ambulatory with basal-bolus insulin therapy and/or GLP1-RA will be  
325 excluded. Patients transiently treated with basal-bolus insulin (standard-of-care treatment)  
326 during hospital admission can be included. Recommendations on insulin adjustment will be  
327 provided at each visit or phone encounter by a study physician.

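### In a parallel trial the sign of the DTSQc cannot show preference between IDegLira and basal-bolus; one interpretive sentence on this secondary outcome needs replacing

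*Combined protocol and SAP*

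**What the plan says.** Specific Aim 3 asks a between-arm question. Its hypothesis begins "Use of IDegLira is associated with higher patient satisfaction and" goes on to adherence, with basal-bolus as the comparator.

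Other Assessments explains how the DTSQc is to be read. The "amplitude of the score on the DTSQc gives the degree of change in satisfaction, while the" "direction (positive or negative) will provide guidance on the preference of one treatment regimen" over the other. The same section sets the timing: the status form (DTSQs) "will be administered at weeks 0, 12 and the DTSQc will be administered at week 26".

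Study Design and Methods describes the design: "The study is a 26-week, open-label, treat-to-target, two-arm parallel, randomized, controlled trial". Patients "will be randomized in a 1:1 manner to receive IDegLira or basal-bolus insulin". Rationale for study design prefers this to a cross-over. On earlier exposure: "Patients previously treated ambulatory with basal-bolus insulin therapy and/or GLP1-RA will be" excluded.

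Two other places bear on the analysis. Endpoints presents the secondary outcomes as comparisons of IDegLira with basal-bolus and lists the DTSQ among them. Statistical Methods sends a continuous outcome measured once to the strategy used for the primary outcome, which starts with Wilcoxon and t-tests between the two groups.

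**The concern.** The sentence in Other Assessments gives the sign of the DTSQc a meaning that the design cannot supply. Within the trial a patient takes IDegLira or basal-bolus, not both. A change score from that patient can compare the assigned regimen only with what came before it, namely oral agents and/or basal insulin.

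Patients enter with HbA1c of 9% or more and have their treatment intensified, so satisfaction could plausibly rise in both arms. Someone writing up Aim 3 who relied on this sentence could report a positive IDegLira score as preference over basal-bolus, although the basal-bolus arm had scored the same. The outcome is self-reported in an open-label trial, so a preference claim should rest on the randomised comparison.

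**Working it through.** **1. What the sign can mean.** By the section's own account the score's size is a degree of change, and the form is given once, at week 26. The document does not name the reference point. The only regimen a patient had before the assigned one is the pre-trial regimen, so a positive sign means more satisfied than on pre-trial treatment. The other study regimen does not enter the score.

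**2. Inputs.** The documents give no DTSQc mean, SD or sample-size figure. The only sample-size figure is for HbA1c: 57 per group. With SD 0.85, margin 0.4, true difference 0 and one-sided alpha 0.05, exact noncentral-t power at 57 is 0.803, so that figure reproduces. The plan recruits 75 per group and expects 20% attrition: 75 × 0.8 = 60 completers per arm. The shared change from pre-trial treatment, d in SD units, is an assumption, ranged from 0 to 0.5. Scores are taken as normal, with the same true mean in both arms.

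**3. Reading signs arm by arm, with no true difference.** The probability that one arm's mean is positive is p = Φ(d√60), with √60 = 7.746. Both means are positive with probability p². The last column is illustrative only: the chance that a one-sample two-sided 5% t-test of the IDegLira arm alone is significantly positive (noncentral t, 59 df, noncentrality d√60). The plan contains no such test.

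| d | d√60 | IDegLira mean > 0 | Both means > 0 | One-sample test of IDegLira arm (not planned) |
|---|---|---|---|---|
| 0 | 0 | 0.50 | 0.25 | 2.5% |
| 0.1 | 0.775 | 0.78 | 0.61 | 12% |
| 0.2 | 1.549 | 0.94 | 0.88 | 33% |
| 0.3 | 2.324 | 0.99 | 0.98 | 63% |
| 0.5 | 3.873 | > 0.999 | > 0.999 | 97% |

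From d = 0.2 upward the sign would nearly always appear to favour both regimens at once, so it cannot separate them. If satisfaction fell equally in both arms, the same figures would apply to negative signs.

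**4. The comparison the plan does contain.** The difference between arm means has expectation d − d = 0, so the shared change cancels. In 40,000 simulated trials with 60 per arm, a two-sample t-test wrongly favoured IDegLira in 2.6%, 2.3% and 2.4% of trials at d = 0, 0.3 and 0.5. Two-sided rejection was between 4.9% and 5.2%.

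**5. Which form is given at week 26.** Other Assessments specifies the DTSQc. The Visit 17 list names the DTSQs. Table 1 has one DTSQ row, marked at weeks 0, 12 and 26, that does not name the form. Other Assessments also compares DTSQs scores from week 0 to week 24, but schedules that form only at weeks 0 and 12.

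**The case against.** The strongest reply is that the analysis plan is already right. Aim 3, Endpoints and Statistical Methods all lead to a between-arm comparison of the DTSQ, and the DTSQc, measured once, falls under the two-sample tests. That stands: the planned comparison does not have this error.

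A reader might infer that the plan contains a rule that would declare IDegLira preferred from its sign alone, with a false-preference rate of 33%, 63% or 97%. The documents do not support this. The sentence speaks of guidance and gives no test, threshold or single-arm analysis, and those percentages belong to a one-sample test that is nowhere planned, at assumed effect sizes.

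The sentence might also be meant as the sign of the between-arm difference, which would be acceptable. That is possible, but as written the direction belongs to the DTSQc score itself and is paired with the amplitude of that same score. If the difference was meant, the text should say so. Nor does the general plan remove the problem: Statistical Methods does not name the DTSQ, so Other Assessments is the specific text that someone interpreting the DTSQc will consult.

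Finally, it would be too strong to say that no patient has ever experienced both regimens. Exclusion criteria 4 and 5 cover only the preceding 3 months, and transient basal-bolus treatment in hospital is allowed. This does not rescue the sentence, because the score is still not a comparison of the two study regimens.

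**Conclusion.** The concern holds as a point of interpretation. The sign of a patient's DTSQc, or of one arm's mean, reflects change from pre-trial treatment and cannot guide a statement about IDegLira against basal-bolus. With equal improvement of 0.2 SD or more and 60 completers per arm, both arms would be positive in at least 88% of trials. That figure rests on normal scores and an assumed d, since the documents give no DTSQc mean or SD; the logical point needs neither.

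The scope is small: one sentence about a secondary outcome. The primary analysis, the sample size and the planned two-sample comparison are unaffected. The sentence still deserves correction because it bears on one of the three Specific Aims and changing it is almost free.

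**What to change.** Replace the sentence in Other Assessments with text to this effect: the sign of the DTSQc describes change from pre-trial treatment only; any statement about IDegLira versus basal-bolus rests on the between-arm difference in mean week-26 DTSQc, with its 95% CI, from a linear model with arm and the week-0 DTSQs score as covariate. The covariate is a modelling choice added to the two-sample comparison already planned, and it uses a baseline score that the trial already collects.

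Reconcile the Visit 17 list with Other Assessments on the form given at week 26, and make Table 1 name the form at each visit. The replacement depends on the DTSQc being collected then. Correct the week-24 reference for the DTSQs at the same time.

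The cost is a short wording amendment. It needs no extra patients or visits, and no new data provided the DTSQc is given at week 26 as Other Assessments states.

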### 866 **Subject Compliance**

867 Subject compliance will be assessed by monitoring of drug accountability. Subjects will be  
868 encouraged at every visit to adhere to the study medications and follow-up schedule. Unused  
869 trial medications will be compared with dispensed amount at each corresponding visit. If  
870 discrepancies are noted, the subject will be asked.

871  
872 **STATISTICAL CONSIDERATIONS:**  
873 **Sample Size Calculation**  
874       The primary outcome is the change in HbA1c from baseline after 26-weeks of treatment.  
875       The primary hypothesis is that HbA1c change is similar between the IDegLira group and the  
876       basal-bolus group. Given the data reported for the DUAL V study, we assume the HbA1c  
877       change from baseline has a standard deviation bounded above by 0.85 (%). We assume the  
878       margin of equivalence is 0.4 (%) and the true mean difference in the primary outcome is 0 (%).  
879       Given 57 subjects per study group, based on a one-sided, two-sample t-tests, we would achieve  
880       80% power to detect non-inferiority, with alpha (type-1 error) set as 0.05. Accounting for 20%  
881       attrition rate of 20%, we need to recruit 75 subjects per group (150 in total).  
882  
883 **Statistical Methods**  
884       This is a randomized, open-label study. We will first compare the primary outcome (i. e.  
885       change in HbA1c from baseline to after 26 weeks of treatment) between the two study groups  
886       using nonparametric and parametric two-sample tests, such as Wilcoxon tests and t-tests. A  
887       logarithm transformation may be employed to make the data better conform to the normality  
888       assumption. We will apply standard variable selection and model checking procedures to decide  
889       the final model.  
890       Secondary outcomes include various measurements (related to glycemic control, quality  
891       of life, adverse effects, and etc.) collected at a single or multiple time points. For continuous  
892       outcomes measured a single time point (i.e. non-longitudinal outcome), we shall analyze them  
893       following the same strategy designed for the primary outcome. For discrete non-longitudinal  
894       outcome, we will use Chi-square (or Fisher's Exact) tests to compare them between the two  
895       study groups. This will be followed by logistic regression or Poisson (or Negative Binomial)  
896       regression to assess other potential confounders. We will perform appropriate model selection  
897       and diagnostic procedures to ensure adequate fit to the data. For outcomes measured at  
898       multiple time points (i.e. longitudinal outcome), we will first conduct cross-sectional analyses as  
899       planned for the non-longitudinal outcomes. Next we will perform repeated measures analyses  
900       that account for with-subject correlations in the longitudinal outcomes. We will analyze  
901       longitudinal continuous outcomes based on repeated measures ANOVA followed by repeated  
902       measures linear regression, and we will analyze longitudinal discrete outcomes by using  
903       repeated measures generalized linear model (GLM). If the assumption of missing completely at  
904       random (MCAR) is reasonable, we shall handle missing data by excluding them from the cross-

905 sectional and the longitudinal data analyses. When MCAR assumption is questionable, we will  
906 assume missing values are missing at random and deal with them by the standard multiple  
907 imputation methods. We plan to conduct statistical analyses using SAS 9.4.

908

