127   12.6% of patients with diagnosed diabetes (18.8 millions)   136

128   have an HbA1c >9%. In the Emory Health Care system   137

129   the largest academic health system in Georgia, over   138

130   64,000 patients have a diagnosis of diabetes, with ~16%   139

131   having an HbA1c>9% (Figure 1). The evidence on the   140

132   management of patients with T2D and very high HbA1c   141

133   very limited, with most studies excluding patients with   142

134   HbA1c > 10%. Figure 1. HbA1c Distribution in Patients   143

135   144

[figure not shown]
136   145

137   146

138   147

139   148

140   149

150       In a recent multi-national study of insulin-naïve patients with T2D, treated with or without  
151   oral agents, showed that only ~40% of patients with HbA1c > 9% were started on basal insulin.  
152   Moreover, the study showed that only 20.9% of such patients achieved HgA1c target (< 7%) at 3  
153   months after initiating basal insulin, indicating a need for coverage of prandial-related  
154   hyperglycemic excursions. Notably, failure to achieve HbA1c targets at 3 months was associated  
155   with an increased risk of not achieving HbA1c targets at 24 months, with < 30% of patients  
156   achieving glycemic targets. This study suggests that providers delayed initiation of basal insulin  
157   as recommended by national guidelines, and frequently failed to intensify therapy to cover  
158   prandial-related hyperglycemic excursions. A recent study in ambulatory patients with T2D and  
159   high HbA1c (>10%) on metformin and sulfonylurea treatment, randomized patients to  
160   combination (COMB) therapy with exenatide plus pioglitazone vs basal-bolus insulin regimen.  
161   COMB provided greater HbA1c reduction at 6 months, with significantly less weight gain.  
162   However, the rates of hypoglycemia were unusually high, up to 56% and 83% in COMB and BB,  
163   respectively. Our group recently validated the efficacy of a hospital discharge algorithm based  
164   on the admission HbA1c. Among those patients with high admission HbA1c> 9% (n: 81), 54  
165   were discharged on basal-bolus insulin regimen. Mean admission HbA1c of 11.1% decreased to  
166   8.8% and to 8.0% after 4 and 12 weeks of hospital discharge (p<0.01), respectively. However, up  
167   to 44% of patients had hypoglycemia (BG < 70 mg/dl) during follow-up. Thus, there is a critical  

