218 hyperglycemia. GLP1-RAs decrease post-prandial glycemic excursions and complement  
219 basal-insulin therapy by enhancing endogenous insulin responses in a glucose-dependent  
220 manner, inhibiting glucagon secretion, slowing gastric emptying and promoting satiety. This  
221 combination has been shown to provide better glycemic control, less hypoglycemia, less weight  
222 gain, and reduce glycemic variability compared to basal bolus therapy or GLP1-RA  
223 alone. IDegLira is a novel fixed-ratio combination of degludec 100 u/ml and liraglutide  
224 3.6 mg in a pre-filled pen. IDegLira has been shown to improve glycemic control, with lower risk  
225 of hypoglycemia, less weight gain, and better patient satisfaction compared to basal-bolus or  
226 stepped-up basal therapy. Pharmacokinetics studies showed that IDegLira provided  
227 coverage over the 24-hours interval at steady levels. In the recent DUAL V trial, IDegLira  
228 resulted in greater HbA1c reduction, weight loss and less hypoglycaemia, compared to up-  
229 titration of insulin glargine in patients with T2D with HbA1c 7-10%. More recently in the DUAL  
230 VII trial, patients with HgA1c 7-10% randomize to IDegLira had similar HbA1c reduction, but  
231 with an 89% reduction in the rate of severe or confirmed symptomatic hypoglycemia and weight  
232 loss compared to basal-bolus insulin. Thus, IDegLira is an attractive and option for patients  
233 with severe hyperglycemia, due to potent HbA1c reduction, lower hypoglycemic risk, and  
234 flexibility of once-daily administration, compared to up to five injections per day in basal-bolus  
235 regimen. However, no previous studies have compared the efficacy and safety of IDegLira in  
236 patients with high HbA1c >9-15%.

237

238

239 **SIGNIFICANCE AND INNOVATION:**

240                   The proposed study will test three innovative questions in patients with poorly controlled  
241                   T2D and HbA1c  $\geq 9\%$ : 1) whether IDegLira, a novel FRC of degludec and liraglutide, results in  
242                   similar glycemic control, 2) less hypoglycemia, less glycemic variability and less weight gain  
243                   compared to a basal-bolus, and 3) whether IDegLira results in better patient satisfaction and  

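### The 0.85 ceiling on the SD of HbA1c change is borrowed from an HbA1c 7-10% trial, and the primary analysis does not pre-specify adjustment for baseline HbA1c

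*Combined protocol and SAP*

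**What the plan says.** Sample Size Calculation takes its variance from one trial: "Given the data reported for the DUAL V study, we assume the HbA1c" "change from baseline has a standard deviation bounded above by 0.85" percentage points. With a margin of 0.4, a true difference of 0 and a one-sided two-sample t-test at 0.05, it states 80% power with 57 per group, and 75 per group (150 in all) after 20% attrition.

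The background section on basal insulin combined with GLP-1 agonists describes DUAL V as a comparison with "titration of insulin glargine in patients with T2D with HbA1c 7-10" percent. Inclusion Criteria for the present trial require HbA1c of 9% to 15%.

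The epidemiology section describes the team's own hospital-discharge cohort: "Among those patients with high admission HbA1c> 9% (n: 81), 54" were sent home on basal-bolus insulin. "Mean admission HbA1c of 11.1% decreased to" 8.8% at 4 weeks and 8.0% at 12 weeks. No SD of change is given.

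For the primary outcome, Statistical Methods plans a comparison "using nonparametric and parametric two-sample tests, such as Wilcoxon tests and t-tests". It adds that a "logarithm transformation may be employed to make the data better conform to the normality" assumption, and then: "We will apply standard variable selection and model checking procedures to decide" the final model. Randomization and Blinding says that randomization is based on HbA1c below 10 or at least 10. Neither baseline HbA1c nor that factor is named as a covariate.

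**The concern.** The two entry ranges overlap only between 9% and 10%, and this trial's range is twice as wide (6 points against 3). The protocol also says that evidence at very high HbA1c is very limited and that IDegLira has not been compared in this range. Those statements leave no basis for an upper bound on the variance in this population. If the true SD exceeds the assumed one, a truly equivalent regimen is more likely to end with an inconclusive Aim 1, after 150 patients and 26 weeks of treatment.

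The second part of the concern is the analysis. Baseline HbA1c can be expected to predict its own change, and adjusting for it removes variance at no cost in patients. The plan allows this through variable selection but does not commit to it, so no gain in power can be counted on. The decision rule is also open. A Wilcoxon test or a log-scale difference does not translate directly into a comparison with 0.4 percentage points, and no confidence bound against 0.4 is named.

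**Working it through.** **Inputs from Sample Size Calculation:** margin 0.4, true difference 0, SD 0.85, one-sided alpha 0.05, 57 evaluable per arm, 20% attrition, 75 recruited per arm. Completers expected: 75 × 0.8 = 60 per arm.

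**Method.** Two-sample t-test with power from the non-central t distribution, df = 2n − 2, non-centrality = 0.4 / (SD × √(2/n)).

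**The plan's own figure.** At n = 57 the standard error is 0.85 × √(2/57) = 0.159 and the non-centrality is 0.4/0.159 = 2.51. The critical t on 112 df is 1.659, which gives power 80.3%. The stated figure reproduces. For attrition, 57/0.8 = 71.25, so 72 per arm would do and 75 is slightly generous.

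**How much room there is.** The largest SD that still gives 80% power is 0.854 at 57 per arm, 0.876 at 60, and 0.981 at 75 (no attrition at all).

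**Unadjusted power.** Every SD other than 0.85 is an assumption.

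| SD of change | 57 per arm | 60 per arm | Completers per arm for 80% | Recruited per arm (÷ 0.8) |
|---|---|---|---|---|
| 0.80 | 84.3% | 85.9% | – | – |
| 0.85 | 80.3% | 82.1% | 57 | 72 |
| 0.90 | 76.2% | 78.1% | 64 | 80 |
| 1.0 | 68.4% | 70.3% | 78 | 98 |
| 1.1 | 61.2% | 63.1% | 95 | 119 |
| 1.2 | 54.9% | 56.8% | 112 | 140 |

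**ANCOVA.** Residual SD = SD × √(1 − r²), where r is the correlation between baseline HbA1c and its change; df = 2n − 4 with the randomization factor included. For example, SD 1.0 with r 0.5 gives 1.0 × √0.75 = 0.866. Power at 60 per arm (every r is an assumption):

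| SD of change | r = 0 | r = 0.3 | r = 0.5 | r = 0.7 |
|---|---|---|---|---|
| 0.85 | 82.1% | 85.1% | 90.6% | 97.4% |
| 1.0 | 70.3% | 73.8% | 80.8% | 92.0% |
| 1.2 | 56.8% | 60.2% | 67.4% | 81.5% |

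The r needed for 80% at 60 per arm is 0.23, 0.48 and 0.68 at SD 0.90, 1.0 and 1.2. At r = 0 nothing material is lost.

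**Simulation check.** 10,000 runs, 60 per arm, randomization stratified at HbA1c 10, assumed normal baseline truncated to 9-15% (realised SD 1.11):

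| SD, r | t-test | ANCOVA |
|---|---|---|
| 0.85, 0.5 | 83.6% | 90.9% |
| 1.0, 0.5 | 70.7% | 80.5% |
| 1.2, 0.5 | 57.5% | 66.9% |
| 1.2, 0.7 | 57.8% | 81.2% |

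With the true difference set at the margin of 0.4, ANCOVA claimed non-inferiority in 4.9%, 5.0% and 5.1% of runs (SD 0.85 with r 0.5; 1.0 with 0.5; 1.2 with 0.7), so the error rate holds.

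**The case against.** The strongest reply is that no underpowering has been shown. The plan presents 0.85 as an assumption, the arithmetic is right, and the documents contain neither an SD for 9-15% nor the SD that DUAL V reported, so 0.85 may already hold a cushion. That stands. The finding is that the bound is unsupported, not that it is wrong.

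The gain from adjustment depends on an unknown r. That also stands. At r = 0.3 the gain is only about 3 points at each SD tabulated, and at an assumed SD of 1.5 even r = 0.7 gives only 65%. Stratifying on HbA1c already captures a little of the benefit: in the simulation at SD 0.85 and r 0.5 the gain is 7.3 points (90.9 − 83.6), against 8.5 by formula (90.6 − 82.1).

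Statistical Methods also provides repeated-measures regression and multiple imputation, which might recover information from dropouts; with all 75 per arm and SD 0.85, power would be 88.9%. That is an upper limit, because imputation does not restore full information. The repeated-measures plan sits in the paragraph on secondary outcomes and does not clearly govern the primary one.

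The discharge cohort is an imperfect source. It had 12 weeks of follow-up after a hospital stay, and it is unclear whether its means describe all 81 patients or the 54 on basal-bolus. It is still closer to the target HbA1c range than a 7-10% trial.

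Finally, variable selection permits adjustment. But in an open-label trial, a primary model chosen after the outcomes are seen is open to challenge, and power cannot be claimed for it in advance.

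**Conclusion.** The concern holds, and the plan should be changed. The 57 per arm follows correctly from its inputs, but the documents do not support 0.85 as an upper bound at HbA1c 9-15%, and the margin for error is thin: 80% power fails above an SD of 0.854 (57 per arm) or 0.876 (60 per arm). Whether the true SD exceeds those limits cannot be settled from the documents. The consequence is confined to power: a larger SD raises the chance of an inconclusive result, not of a false claim.

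The better-supported half is the missing commitment to one baseline-adjusted primary analysis. That change helps even if 0.85 is correct and costs essentially nothing if the correlation is zero. It reduces the risk from a larger SD but does not remove it. The rewording of the SD assumption is minor by comparison.

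**What to change.** 1. In Statistical Methods, name one primary non-inferiority analysis: ANCOVA of the week-26 change in HbA1c on treatment, baseline HbA1c and the randomization factor (below 10, or 10 and above). Non-inferiority is claimed if the one-sided 95% upper confidence bound for IDegLira minus basal-bolus lies below 0.4. For the primary outcome this replaces the t-test and Wilcoxon tests, the optional log transformation and variable selection; those may stay as labelled sensitivity analyses.

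2. In Sample Size Calculation, state that the SD is assumed to be 0.85 rather than bounded by it. Report beside it the SD of change in the team's own cohort with HbA1c above 9%, if it can be obtained, noting the 12-week follow-up and which patients it covers. Add a power table over SD 0.85 to 1.2, labelled as assumptions.

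**Cost:** wording in two sections. No extra patients, visits or samples are needed, since baseline HbA1c is already measured and used in randomization. The team gives up choosing the primary model after seeing the data, and the power table may look less favourable. By comparison, securing 80% without adjustment would take 98 recruited per arm at SD 1.0, or 140 at SD 1.2, against 75 now.

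### The trial is sized on a one-sided t-test against a 0.4-point margin, but Statistical Methods names no deciding primary analysis, so analyses that follow the plan can disagree on non-inferiority

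*Combined protocol and SAP*

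**What the plan says.** Specific Aim 1 frames the primary comparison as "glycemic control, as measured by change in HbA1c (non-inferiority limit of 0.4" percentage points, and the Endpoints section repeats that limit. Sample Size Calculation states the intended test: "Given 57 subjects per study group, based on a one-sided, two-sample t-tests, we would achieve" "80% power to detect non-inferiority, with alpha (type-1 error) set as 0.05". It assumes an SD of at most 0.85, a true difference of 0 and a "margin of equivalence is 0.4".

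Statistical Methods opens with "We will first compare the primary outcome", to be done "using nonparametric and parametric two-sample tests, such as Wilcoxon tests and t-tests". It adds that a "logarithm transformation may be employed to make the data better conform to the normality" assumption, and then: "We will apply standard variable selection and model checking procedures to decide" the final model. For the primary outcome it gives no margin, side, alpha or confidence interval. Its last sentences let missing data be excluded if missing completely at random seems reasonable, and otherwise be multiply imputed. Randomization and Blinding says that randomization is based on HbA1c, below 10 versus 10 or above.

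**The concern.** A sizing assumption is not a decision rule. An analyst following Statistical Methods could report a t-test, a Wilcoxon test or a covariate-selected model as the primary result and comply each time. If these differ, nothing says which one stands. The trial is open-label, so a choice made after the data are seen would be hard to defend. The same strategy is also extended to continuous secondary outcomes measured at one time point.

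The log option has its own difficulty. The outcome is a change score, and a log is undefined for changes of zero or of the wrong sign, whichever way change is coded. If HbA1c itself is logged instead, a 0.4-point margin has no single equivalent.

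**Working it through.** **1. The plan's own figure.** Inputs from Sample Size Calculation: margin 0.4, SD 0.85, true difference 0, one-sided alpha 0.05, power 80%.

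- Normal approximation: n = 2 × (1.645 + 0.842)² × 0.85² / 0.4² = 55.8, so 56 per arm.
- Exact t-test at 57 per arm: standard error = 0.85 × √(2/57) = 0.159; noncentrality = 0.4 / 0.159 = 2.51 on 112 degrees of freedom; power 80.3% (79.7% at 56). The stated 57 is reproduced.
- Attrition: 57 / 0.8 = 71.25, so 72 per arm would do. The planned 75 leave 75 × 0.8 = 60, with power 82.1%.

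**2. t-test against Wilcoxon.** Simulated trials, 57 per arm, SD 0.85, both tests one-sided 0.05 against 0.4, true difference 0. With normal data they reach opposite conclusions in 5.0% to 5.5% of trials. With skewed (gamma) or heavy-tailed (t, 4 df) data, both assumed shapes, the figure is about 11%.

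**3. t-test against a selected model.** Normal data and three baseline covariates, with backward selection at p<0.05 and treatment forced in. Stratified allocation is balanced within two baseline-HbA1c strata cut at the median, which is an assumed split (20,000 runs per setting). Unstratified settings use 40,000 runs. The documents give no correlations with outcome, so four pairs are assumed: baseline HbA1c / each of the two other covariates. The fixed model contains treatment, baseline HbA1c and stratum. False non-inferiority is evaluated at a true deficit of 0.4; disagreement and power at a true difference of 0.

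| Result (%) | 0/0 | 0.3/0.1 | 0.4/0.2 | 0.6/0.2 |
|---|---|---|---|---|
| t-test and selected model disagree, stratified | 0.7 | 5.1 | 9.2 | 13.0 |
| t-test and selected model disagree, unstratified | 0.7 | 7.0 | 11.5 | 16.2 |
| False non-inferiority, selected model, stratified | 5.3 | 5.2 | 5.4 | 5.2 |
| False non-inferiority, selected model, unstratified | 5.1 | 5.1 | 5.3 | 5.4 |
| False non-inferiority, t-test, stratified | 5.2 | 4.6 | 4.2 | 3.1 |
| False non-inferiority, fixed model, stratified | 5.2 | 5.1 | 5.1 | 5.3 |
| Power, t-test, stratified | 81.0 | 80.9 | 81.8 | 83.1 |
| Power, fixed model, stratified | 80.7 | 83.0 | 86.1 | 92.6 |

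Simulation error on a 5% rate at 20,000 runs is √(0.05 × 0.95 / 20,000) = 0.15 percentage points.

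**4. Log scale.** Matching 0.4 points at an HbA1c of 7% gives a ratio of 7.4 / 7.0 = 1.057, which at 9% is 9 × 0.0571 = 0.51 points. Matching at 9% gives 9.4 / 9.0 = 1.044, which at 7% is 7 × 0.0444 = 0.31 points.

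**The case against.** The best defence is that the plan is more ordered than it looks. The sizing paragraph fixes test, side, alpha and margin. Statistical Methods does the two-sample comparison first, and for discrete outcomes it says that the regression which follows is there to look at confounding. By analogy, the sized t-test decides and the model is a check. This is the natural reading and it narrows the gap, but it remains an inference. Nothing ranks the t-test above the Wilcoxon test, and the model is the one called final.

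It is also fair to say that naming the unadjusted t-test would settle the choice of test with the smallest edit. Its reduced error under stratified allocation is conservative, not dangerous. The case for adjustment is precision, and its size depends on assumed correlations.

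A third objection stands in full: naming a test does not by itself leave one analysis, because the choice between exclusion and imputation stays open. With 75 per arm, 20% random loss, the adjusted model and a true difference of 0, the two approaches disagreed on non-inferiority in 2.2% to 5.6% of simulated trials (3,000 runs per setting). The assumed correlations were 0 or 0.4 for baseline and 0 to 0.7 for an auxiliary variable. The fix has to cover this.

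**Conclusion.** The concern holds as a gap in specification. The plan states what it intends to test but not which analysis decides. The textual gap needs no simulation; the rates do. About 5% disagreement between t-test and Wilcoxon assumes normal data. The range of about 1% to 16% for a selected model also rests on correlations and a covariate set that are not in the documents.

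Three stronger readings are tempting and are not supported.

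- **Serious inflation of the 5% error.** Ordinary selection gives 5.1% to 5.4%. Taking the most favourable of eight covariate models would give 6.0% to 10.4%, and reading a non-significant two-sided t-test as similarity would give 29.8% at a true deficit of 0.4. The plan proposes neither rule.
- **Unclear direction, or an equivalence trial.** The words similar and equivalence are loose, but the one-sided test and the single limit make the direction plain.
- **A wrong sample size.** The stated 57 per arm is reproduced.

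What is at stake is an undetermined primary conclusion and some lost precision. It should be fixed before the data are analysed.

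**What to change.** Name one primary analysis: a linear model of untransformed 26-week change in HbA1c, in percentage points, with treatment, baseline HbA1c and randomization stratum (below 10, or 10 and above). Conclude non-inferiority only if the upper limit of the two-sided 90% confidence interval for IDegLira minus basal-bolus is below 0.4, which keeps the planned one-sided 0.05. For the primary outcome, remove the log-transformation and variable-selection options. Make the unadjusted t-test and a Wilcoxon test shifted by 0.4 sensitivity analyses. State the analysis population and a single missing-data method in advance, in place of the present conditional choice. Use the term non-inferiority throughout.

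The cost is an edit to the combined protocol and SAP. Sample size, visits and data collection are unchanged. If the covariates do not predict change, the model loses under one point of power against the t-test: 80.7% against 81.0% stratified, 80.0% against 80.6% unstratified. If baseline HbA1c correlates 0.4 with change (assumed, with 0.2 for each of the other two covariates), it gains 86.1 − 81.8 = 4.3 points under stratified allocation.
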